12.2.3 Scatterplots of laboratory tests

Scatterplots of measurements before and after treatment will be presented.

Assessment time points: Week 0 and end of the treatment period

12.3 Vital Signs and Body Weight

Analysis items are shown below.

Vital signs: Systolic blood pressure, diastolic blood pressure, pulse rate, and body temperature Body weight (before dialysis)

12.3.1 Vital Signs and Body Weight

Summary statistics will be presented.

Assessment time points: Shown in Table 12.3.1-1.

Table 12.3.1-1 Assessment Time Points

Item	Assessment Time Points	
Vital signs	Weeks -2, 0, 1, 2, 4, and 8, end of the treatment period, and Follow-up	
	Week 2	
Body weight	Weeks -2, 0, and 8, and end of the treatment period	

12.3.2 Scatter plots of vital signs and body weight

Scatterplots of measurements before and after treatment will be presented.

Assessment time points: Week 0 and end of the treatment period

12.4 Dependency Assessment

12.4.1 Evaluation of dependency based on judgment by dependency assessment members

The numbers and percentages of subjects will be presented by category in Table 12.4.1-1. However, only subjects with dependence will be included in the tabulation of severity.

Table 12.4.1-1 Category

Item	Category
Dependency	Negative, positive, not evaluable
Severity	Mild, moderate, severe

Statistical Analysis Dlan	Protocol No. MR13A9-4
Statistical Analysis Plan	Version: 1.0

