Reported serious adverse events included the following: 2 events (encephalopathy and shunt stenosis) in 2 subjects in the 0.25 μ g/kg group, 8 events (abdominal distension, influenza, diverticulitis, dizziness, hyperglycaemia, cholecystitis, hypotension, and muscular weakness) in 4 subjects in the 0.5 μ g/kg group, and 1 event (dizziness) in 1 subject in the 1.5 μ g/kg group. Of these events, relationship to study treatment was not ruled out for 4 events (diverticulitis, dizziness, hypotension, and hyperglycaemia) in 3 subjects in the 0.5 μ g/kg group and 1 event (dizziness) in 1 subject in the 1.5 μ g/kg group. Study treatment was discontinued or interrupted due to 1 event in 1 subject in the 0.25 μ g/kg group, 2 events in

2 subjects in the 0.5 μ g/kg group, 1 event in 1 subject in the 1.0 μ g/kg group, and 17 events in 10 subjects in the 1.5 μ g/kg group. Dependency was assessed as being present in 2 subjects in the placebo group and 1 subject in the MR13A9 0.5 μ g/kg group.

In a non-Japanese phase II clinical study (CR845-CLIN2005 Part B), 65 hemodialysis patients with moderate to severe pruritus received intravenous doses of MR13A9 1.0 μ g/kg or placebo 3 times weekly for 2 weeks. With respect to efficacy, the primary endpoint of change in VAS (i.e., change from baseline in the mean VAS for the most intense itching at Week 2) (mean \pm standard deviation) was -33.1 ± 23.03 mm in the 1.0 μ g/kg group versus -21.5 ± 24.79 mm in the placebo group. With respect to safety, the incidence of adverse drug reactions was 9.4% (3/32 subjects) in the placebo group and 18.2% (6/33 subjects) in the 1.0 μ g/kg group. Commonly reported adverse drug reactions (in \geq 5% of subjects in the MR13A9 group) included dizziness, hypoaesthesia, and pruritus.

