Appendix 8 Dependency assessment

Questionnaire on the study drug (before dialysis at Week 8 or at the time of discontinuation)

Question	Remarkable	Moderate	Slight	None	Remarks Specify reason for Remarkable and Moderate
Do you feel clearheaded when using the study drug?					
Do you feel indifferent to disliked persons or things when using the study drug?					
Do you become hyperactive or talkative when using the study drug?					
Do you become broad-minded when using the study drug?					
Do you feel intoxicated when using the study drug?					
Do you feel irritable or somewhat lonely when the effect of the study drug runs out?					
Do you want to continue using the study drug?					☐ To relieve pruritus☐ To improve mood
Do you think this drug has become less effective?					
Do you want to use the study drug in larger doses?					☐ To relieve pruritus☐ To improve mood
Do you feel nauseated or tremulous when the effect of the study drug runs out?					-

Adapted from Literature Reference 18)

Questionnaire on the study drug (at Week 9 or at Week 1 after discontinuation)

Question	Remarkable	Moderate	Slight	None	Remarks Specify reason for Remarkable and Moderate
Did you feel irritable or unstable after					
you discontinued the study drug?					
Did you have more difficulty in					
sleeping after you discontinued the					
study drug?					
Did you have nausea, vomiting,					
tremors of limb or perspiration after					
you discontinued the study drug?					
Do you really want to use the study					☐ To relieve pruritus
drug?					☐ To improve mood
Did you have convulsions after you					
discontinued the study drug?					
Did you have a clouded mind or heard					
or seen anything unusual after you					
discontinued the study drug?					

Adapted from Literature Reference 18)

CERTIFICATE OF TRANSLATION

This document is the translated version of the source document below written in Japanese. It is hereby certified that this document is a true and accurate translation of the source document from Japanese into English.

Source document: MR13A9-4 Clinical Study Protocol (Ver 02.00.000)

File name: mr13a9-4-p-jp.pdf

Name of representative:

Signature and Date of signature: Refer to Signature Page

SIGNATURE PAGE

Document ID: 090186a1801125b3

User	Date(UTC)	Reason
		,

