All statistical tests will be performed using a two-sided significance level of 5%; however, a two-sided significance level of 15% will be used for the analysis of between-group imbalance. Summary statistics will be presented as the number of subjects, mean, standard deviation, minimum, median, maximum, and quartile. Unless otherwise specified, data will be tabulated by group and by time point. Week 0 will be the baseline.

SAS System Release 9.4 for Windows (SAS Institute Inc.) will be used to conduct the analysis.

4. Analysis Sets

The analysis sets are defined as follows. When the full analysis set (FAS) and the per protocol set (PPS) are used as analysis sets, analyses will be performed based on the treatment group to which each subject has been allocated. When the safety set (SS) and the pharmacokinetic analysis set (PKS) are used as analysis sets, analyses will be performed based on the treatment group in which each subject has been actually treated.

- FAS: Population of subjects, excluding the following subjects: subjects with GCP violations, untreated subjects, discontinued subjects before entry to the treatment period, some of the ineligible subjects, and subjects with no available mean NRS score at baseline (Week 0)
- PPS: Population of subjects, excluding the following subjects from the FAS: ineligible subjects, discontinued subjects, deviators, and subjects with broken emergency key codes, as the subjects to be excluded from the PPS

Statistical Analysis Plan	Protocol No. MR13A9-4
	Version: 1.0

- SS: Population of subjects, excluding the following subjects: subjects with GCP violations, untreated subjects, and discontinued subjects before entry to the treatment period
- PKS: Population of subjects, excluding the following subjects from the SS: subjects with no available plasma drug concentration data

Correspondence of the analysis items and the analysis sets is shown in Table 4-1.

Table 4-1 Analysis Items and Analysis Sets

Endpoints	Analysis items	Analysis sets
Demographic and other baseline	Subject demographics	FAS, PPS, SS, PKS
characteristics	Other	SS
Treatment compliance	All items	FAS, SS
Efficacy	Primary variable (primary analysis)	FAS (primary analysis set), PPS
	Other	FAS
Pharmacokinetics	All items	PKS
Safety	All items	SS

5. Analysis Groups

- MR13A9 0.25 μg/kg group: Subjects allocated to or treated with MR13A9 0.25 μg/kg
- MR13A9 0.5 μg/kg group: Subjects allocated to or treated with MR13A9 0.5 μg/kg

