12.1 Adverse Events and Adverse Drug Reactions

Unless otherwise specified, the following events will be tabulated.

- Events occurring between the start of study treatment and the end of the follow-up period
- Events occurring between the start of study treatment and the end of the treatment period
- Adverse events of special interest occurring between the start of study treatment and the end of the follow-up period
- Adverse events of special interest occurring between the start of study treatment and the end of the treatment period

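### Dependency severity percentages are taken among dependent subjects only and are not comparable between arms; the questionnaire items and event onset after treatment have no table of their own

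*SAP*

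**What the plan says.** Dependency is a declared safety endpoint (Protocol 3.2.1), chosen because opioids could affect it (Protocol 3.2.2). Protocol 13.6.4 promises only the number and percentage of subjects with and without dependency.

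SAP 12.4 has a single subsection, 12.4.1, which is based on the members' judgement: "The numbers and percentages of subjects will be presented by category in Table 12.4.1-1". The dependency row of that table has the categories "Negative, positive, not evaluable". The severity row has mild, moderate and severe, with the restriction "However, only subjects with dependence will be included in the tabulation of severity". No time point is named there. The general rule in SAP section 3 is "Unless otherwise specified, data will be tabulated by group and by time point".

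Protocol Appendix 8 has two questionnaires: 10 items at Week 8 or discontinuation, and 6 items at Week 9 or one week after discontinuation. Every item has four levels. Under Protocol 9.9 the members judge from the questionnaire, by a separate procedure that is not part of these documents.

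SAP 12.1 tabulates adverse events in two windows. One runs to the end of follow-up. The other is "Events occurring between the start of study treatment and the end of the treatment period". Both begin at the first dose, and the same pair is used for adverse events of special interest.

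**The concern.** Whether a subject is judged dependent is itself an outcome after randomisation. A percentage taken only among such subjects has a denominator that treatment can change. If a dose produces more mild dependence, its share of severe cases falls even when the number of severe cases rises. The study's objective includes dose-response for safety, so the severity row will be read across doses, and it could point the wrong way.

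Two further gaps concern the same endpoint. No table in Protocol 13.6 or SAP 12, and no list in SAP 13, presents the Appendix 8 answers. Three items (wanting to continue, wanting larger doses, really wanting the drug) carry boxes that separate relief of pruritus from improvement of mood. For an antipruritic drug that distinction matters when a positive judgement is interpreted, and the planned categories do not show it. Withdrawal effects would appear after stopping, yet no event window begins there.

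**Working it through.** SAP 12.4.1 gives no rate, sample size or power, so there is no planned figure to reproduce.

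**Inputs**
- 60 subjects per group (Protocol 7.6.1), taken as the SS size per arm.
- Earlier Japanese study MR13A9-3 (Protocol 1.3.2.2): "Dependency was assessed as being present in 2 subjects in the placebo group and 1 subject in the" 0.5 μg/kg group. No positives are mentioned for the other doses.
- Group sizes from the adverse drug reaction denominators in the same section: placebo 21; active 21 + 21 + 19 + 23 = 84. I assume that these also apply to the dependency judgement.

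**Step 1: expected size of the severity denominator**

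Expected positives = 60 × rate.

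| Assumed rate | Exact 95% CI | Positives per 60 | P(10 or more) |
|---|---|---|---|
| All active, 1/84 = 1.2% | 0.0 to 6.5% | 0.7 | 0.000 |
| 0.5 μg/kg, 1/21 = 4.8% | 0.1 to 23.8% | 2.9 | 0.001 |
| Placebo, 2/21 = 9.5% | 1.2 to 30.4% | 5.7 | 0.056 |

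At 1/84 the chance of at least one positive in an arm is 1 − (83/84)^60 = 0.513. In about half of such arms there would be no severity percentage at all.

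**Step 2: what the two denominators show**

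Severe/N = (positive/N) × (severe/positive). The SAP reports the last factor, which can move against the product. The counts below are assumed, to show the mechanism.

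| Arm | Positive | Severe | % of positives (95% CI) | % of 60 (95% CI) |
|---|---|---|---|---|
| Placebo | 1 | 1 | 100 (2.5 to 100) | 1.7 (0.0 to 8.9) |
| Active | 6 | 3 | 50.0 (11.8 to 88.2) | 5.0 (1.0 to 13.9) |

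The order reverses. It also reverses if the two arms are swapped, which is closer to the earlier study's pattern of more positives on placebo: active then shows 100% against 50%, although it has fewer severe cases. With 6 positives, one subject moves the conditional percentage by 1/6 = 16.7 points and the SS percentage by 1/60 = 1.7 points. Neither version is evidence of a difference (Fisher's exact p = 1.0 among positives, 0.62 over 60 per arm). The point is the direction that the table displays.

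**Step 3: onset after treatment**

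Let E and S be the events and the subjects with events to the end of follow-up, and E_T and S_T the same to the end of treatment.
- Events with later onset = E − E_T, which the planned output gives.
- S − S_T counts only subjects whose first event came after treatment. A subject with events in both periods is in S and in S_T and cancels out. The difference is therefore only a lower bound on the number of subjects with onset after treatment.
- SAP 12.1.5 splits events of special interest by the period in which they resolved, not the period in which they began.

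**The case against.** The strongest reply is that most of this can be recovered from what is planned. SAP 12.4.1 gives numbers as well as percentages, so severity per treated subject is one division away. Subjects who are not dependent have no severity grade, so restricting the severity rows is ordinary practice, and with so few cases a careful reader will use the counts. The SAP already gives more than Protocol 13.6.4 promised.

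This stands in part, and it rules out several stronger readings that a reader might infer:
- *Severity cannot be compared across doses.* Not supported: the counts allow it. Only the planned percentage misleads.
- *The questionnaire data go unused.* Not supported: Protocol 9.9 makes them the basis of the members' judgement. What is missing is any display of the answers themselves. Raw item levels could mix efficacy with dependence, so a table should carry the reason boxes.
- *Nothing after stopping is tabulated.* Not supported: adverse events run to the end of follow-up, laboratory tests and vital signs are summarised at Follow-up Week 2, and later event counts follow by subtraction. Events of special interest are also listed individually (SAP 13), and these include seizures, mental status change and mood changes.
- *There is only one overall judgement.* Not established: the default layout is by time point, and 12.4.1 neither names a time point nor overrides the default. Whether Week 8 and Week 9 are judged separately is unclear.

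**Conclusion.** The point holds for the planned severity percentage. It conditions on a post-randomisation outcome, would usually rest on about 0 to 6 subjects per arm, and can reverse the order of the arms. The range of 0.7 to 5.7 assumes that the earlier study's rates carry over from 2 weeks of treatment to 8. Those rates come from 3 positives in 105 subjects and are imprecise. The reversal uses assumed counts: 1 and 6 positives are roughly the ends of that range, not a prediction.

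It also holds that neither questionnaire has an item-level table or listing, and that the number of subjects with event onset after treatment is not a planned output. How the members judge and grade severity may be defined in the separate procedure, which would not change the denominator.

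The consequence is limited to descriptive safety reporting on a declared endpoint. It is worth correcting because the data are already collected.

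**What to change.** 1. **SAP 12.4.1, severity.** Tabulate none, mild, moderate, severe and not evaluable with the SS as denominator, in place of the restriction to dependent subjects.
2. **SAP 12.4.1, timing.** State the time point or time points of the members' judgement.
3. **SAP 12.4, new table.** Show each Appendix 8 item by its four levels and by group, separately for Week 8 or discontinuation and for Week 9 or Week 1 after discontinuation. Include the pruritus and mood reason boxes for the three items that have them.
4. **SAP 12.1, new window.** Add events with onset after the end of the treatment period, with subjects entering follow-up as denominator.

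The cost is SAP wording and a few more descriptive tables without error control. No new data collection is needed.

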12.5 Safety Subgroups

The same analysis as "12.1.1 Incidence of adverse events and adverse drug reactions" will be performed for each subgroup shown in Table 12.5-1.

Table 12.5-1 Subgroups

Item	Category
Sex	Male, female
Age	< 65 years, ≥ 65 years
Prior treatment with nalfurafine hydrochloride	No, Yes
Specific signs or symptoms to be confirmed in the screening period	No, Yes

13. Tabulated Lists

The following lists will be prepared for subjects who entered the treatment period. However, the lists will not be prepared if there is no applicable event.

- Deaths
- Serious adverse events excluding deaths
- Adverse events leading to interruption
- Adverse events leading to discontinuation during the treatment period
- Adverse events of special interest
- Abnormal laboratory values by subject

14. History of Preparation

Prepared on January 20, 2020 Version: 1.0

CERTIFICATE OF TRANSLATION

This document is the translated version of the source document below written in Japanese. It is hereby certified that this document is a true and accurate translation of the source document from Japanese into English.

Source document: MR13A9-4 Statistical Analysis Plan (Ver 1.0)

File name: mr13a9-4-s-jp-p.pdf

Name of representative:

Signature and Date of signature: Refer to Signature Page

SIGNATURE PAGE

Document ID: 090186a1801125b5

User	Date(UTC)	Reason
		,
